## **10.3 Additional Efficacy Analyses**

The following additional efficacy variables will be summarized at all Extended dosing period visits:

- Proportion of subjects achieving PASI 50/75/90/100
- Proportion of subjects achieving the sPGA score of clear or almost clear
- Change from baseline in Pain-VAS (in subgroup of patients with diagnosed and suspected psoriatic arthritis)
- Change from baseline in DLQI.

- Proportion of subjects achieving DLQI score of 0 and 0/1;

## **11.0 Safety Analysis**

### **11.1 General Considerations**

Safety analyses will include adverse events, clinical laboratory, local tolerability, and vital sign measurements.

### **11.2 Analysis of Adverse Events**

#### **11.2.1 Treatment Emergent Adverse Events**

Treatment emergent adverse events (TEAEs) are defined as any event with an onset that is after the first dose of risankizumab in this study and with an onset date within 105 days after the last dose of study drug in the analysis period.

Events where the onset date is the same as the study drug start date are assumed to be treatment emergent, unless the adverse event start time is prior to the study drug start time. If an incomplete onset date is collected for an adverse event, the event will be assumed to be treatment-emergent unless there is other evidence that confirms that the event is not treatment-emergent (e.g., the event end date is prior to the study drug start date).

The number and percentage of subjects experiencing treatment-emergent TEAEs will be tabulated using the Medical Dictionary for Drug Regulatory Activities (MedDRA®) system organ class and preferred term.

Considering the fact that some subjects had dose escalation due to lack of efficacy at EV2, selected safety tables will be generated breaking down by the group of subjects who remained at 90 mg throughout the study, the group of subjects who received 180 mg at EV2, and total.

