7. "xT" is a targeted physical examination including assessment of vital sign measurements, and evaluation of organ systems associated with AE(s) symptoms or laboratory abnormalities.
8. Measured after 5 minutes of rest in the supine position. Measurements of vital signs should, if possible, always precede blood sampling.
 - a. Extended visit 1: Vital signs will be taken ~ 30 min pre-dose, 5 minutes, and 1 hour after the dose is administered
 - b. Following dosing visits: Vital signs will be taken ~ 30 min pre-dose, 5 minutes, and 1 hour after the dose is administered
 - c. Non-dosing visit (Extended EOS): Vital signs will be measured once per visit
9. ECG to be performed after 5 minutes of rest in the supine position, at every 24 weeks, starting from EV1 (EV1, EV3, EV5...). Should, if possible, be performed prior to blood sampling.
10. Not to be performed for patients who prematurely discontinue the treatment period.
11. All new AEs as well as unresolved AE from the preceding trial 1311.2 should be followed up within this study.
12. Only for patients with psoriatic arthritis.
13. For details of laboratory tests cf. [Section 5.2.3](#), [Table 5.2.3:1](#) and [5.2.3.2](#)
14. Patients must be fasting for at least 8 hours prior to collection of the safety laboratory samples.
15. Only applicable for women of childbearing potential.
16. In women of childbearing potential urine pregnancy test has to be performed before each administration of study drug.
17. Blood samples for protein biomarker, PK and ADA will be drawn ~ 30 min before the subcutaneous injection (PreD) at every 24 weeks, starting from EV1 (EV1, EV3, EV5...).
18. For patients who prematurely discontinue the follow up period before study end (for any reason), an early Extended EOS visit is required. This early Extended EOS visit will include the same procedures as the normal Extended EOS visit.
19. Patients will be asked to give consent to be contacted (or for their primary care physician to be contacted) by the study team to obtain vital status information preferably at the time of study entry
20. Only required at EV1 for patients who are having EV1 as their first 1311.13 visit
21. All efficacy assessments should be performed pre-dose (PreD)
22. To be repeated once per year until study end (EV1, EV5, EV10...)

Proprietary confidential information.

© 2018 Boehringer Ingelheim International GmbH or one or more of its affiliated companies. All rights reserved.

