5.2.2 Assessment of adverse events

5.2.2.1 Definitions of adverse events

Adverse event

An adverse event (AE) is defined as any untoward medical occurrence, including an exacerbation of a pre-existing condition, in a patient in a clinical investigation who received a

Proprietary confidential information.

© 2018 Boehringer Ingelheim International GmbH or one or more of its affiliated companies. All rights reserved.

This document may not - in full or in part - be passed on, reproduced, published or otherwise used without prior written permission.

pharmaceutical product. The event does not necessarily have to have a causal relationship with this treatment.

Serious adverse event

A serious adverse event (SAE) is defined as any AE which results in death, is immediately life-threatening, results in persistent or significant disability / incapacity, requires or prolongs patient hospitalisation, is a congenital anomaly / birth defect, or is to be deemed serious for any other reason if it is an important medical event when based upon appropriate medical judgement which may jeopardise the patient and may require medical or surgical intervention to prevent one of the other outcomes listed in the above definitions.

Intensity of adverse event

The intensity grading of AEs will be performed according to Rheumatology Common Toxicity Criteria (RCTC) Version 2.0 developed by Outcome Measures in Rheumatology (OMERACT) ([R13-3515](#)). Cf. [Appendix 10.7](#) and ISF for intensity/severity classification.

Causal relationship of adverse event

Medical judgment should be used to determine the relationship, considering all relevant factors, including pattern of reaction, temporal relationship, de-challenge or re-challenge, confounding factors such as concomitant medication, concomitant diseases and relevant history. Assessment of causal relationship should be recorded in the case report forms.

Yes: There is a reasonable causal relationship between the investigational product administered and the AE.

No: There is no reasonable causal relationship between the investigational product administered and the AE.

Worsening of the underlying disease or other pre-existing conditions

Worsening of the underlying disease or of other pre-existing conditions will be recorded as an (S)AE in the (e)CRF.

Changes in vital signs, ECG, physical examination, and laboratory test results

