5.2.2.2 Adverse event and serious adverse event reporting

All adverse events, serious and non-serious, occurring during the course of the clinical trial (i.e., from signing the informed consent onwards through the Residual Effect Period (REP) /Extended follow-up period) will be collected, documented and reported to the sponsor by the investigator on the appropriate CRF(s) / eCRFs / SAE reporting forms. Reporting will be done according to the specific definitions and instructions detailed in the ‘Adverse Event Reporting’ section of the Investigator Site File.

Reporting of Adverse Events in Remote Data Capture system (RDC):

AEs that are ongoing at the end of the previous trial (1311.2) will have to be re-entered, and any adverse events that have started between the two trials (in the event that the 6 weeks time-window is used), will also be entered into the 1311.13 RDC system.

Reporting of Adverse Events on the SAE form:

Specific instructions for the SAE reporting process concerning SAE forms in previous and roll-over studies will be provided in the ISF.

The REP for BI 655066 is 12 weeks. Therefore, all events reported within 12 weeks of the last trial medication will be considered on treatment. All adverse events will be reported up until the last per protocol visit (Extended EOS visit), which is 84 (+7 days) days after the last dose of trial medication.

The investigator does not need to actively monitor patients for AEs once the clinical trial has ended. However, if the investigator becomes aware of an SAE(s) that occurred after the patient has completed the clinical trial (including any protocol required REP and / or follow-up), it should be reported by the investigator to the sponsor if considered relevant by the investigator.

For each adverse event, the investigator will provide the onset date, end date, intensity, treatment required, outcome, seriousness, and action taken with the investigational drug. The

Proprietary confidential information.

© 2018 Boehringer Ingelheim International GmbH or one or more of its affiliated companies. All rights reserved.

This document may not - in full or in part - be passed on, reproduced, published or otherwise used without prior written permission.

investigator will determine the relationship of the investigational drug to all AEs as defined in [Section 5.2.2.1](#).

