- Inclusion criteria 3 (Negative serum β -Human Chorionic Gonadotropin (β -HCG))
Exclusion criteria 8 (Any clinically significant laboratory abnormalities)

Check consistency in medical history with the data obtained at visit 1 of the previous trial. All changes in medical history must be documented as adverse events and will be followed up as such during this trial.

Re-record ongoing adverse events/concomitant medications from the previous trial and record any adverse events/concomitant medications that may have started between the two trials, in the event that the 6 week time-window between trials was used.

All patients will be administered 90 mg BI 655066 s.c. at Extended visit 1.

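### The TEAE definition has no worsening criterion, so an adverse event carried over from 1311.2 that keeps its old onset date stays out of the TEAE outputs even if it worsens, turns serious or ends treatment here

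*SAP*

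**What the plan says.** The start of the TEAE window is in SAP 11.2.1: "Treatment emergent adverse events (TEAEs) are defined as any event with an onset that is after the first dose of risankizumab in this study". The end is also set by onset: "with an onset date within 105 days after the last dose of study drug in the analysis period". Two refinements follow. An event on the first-dose day counts unless its start time precedes the dose. For partial dates, "If an incomplete onset date is collected for an adverse event, the event will be assumed to be treatment-emergent unless there is other evidence" to the contrary. Both still classify by when the event began.

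The protocol brings earlier events into this study's database. Section 5.2.2.2 says "AEs that are ongoing at the end of the previous trial (1311.2) will have to be re-entered", Section 6.2.2.1 says "Re-record ongoing adverse events/concomitant medications from the previous trial", and Flow Chart footnote 11 says "All new AEs as well as unresolved AE from the preceding trial 1311.2 should be followed up within this study". For each event, Section 5.2.2.2 collects an onset date, end date, intensity, seriousness and action taken with study drug.

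Section 5.2.2.1 defines an adverse event as "any untoward medical occurrence, including an exacerbation of a pre-existing condition" and adds that worsening of pre-existing conditions goes into the case report form as an adverse event, serious or not.

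**The concern.** Events with onset before the first dose in this study are a built-in feature of a roll-over design. A definition that looks only at onset treats such an event as not treatment-emergent whatever happens to it later. Most TEAE definitions avoid this by adding worsening after first dose; this one does not.

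Occurrence of AEs, drug-related AEs and SAEs are the primary safety endpoints (Protocol 5.2.1.1 and 7.3.1), and the study is descriptive, so the tabulated percentages and rates are the result. With about 100 patients, rows such as severe TEAEs or TEAEs leading to discontinuation may be sparse, and a few omitted patients could be visible there. Where 1311.2 treatment was not risankizumab (about 25% of that trial's patients, since Protocol 2.3 gives 75% on risankizumab), a change on first exposure to the drug could go uncounted.

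**Working it through.** The plan states no figure on this point, so the check is a reading of the rules against each other.

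**Step 1: trace a carried-over event through the rules.** Take an event that began in 1311.2, is still open at roll-over and is re-entered here.

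- *It rises in grade and the re-entered record is updated.* Onset is before the first dose here, so it is not a TEAE. Regrading of an open event is plausible: the general grade descriptions in Protocol Appendix 10.7 rest partly on duration and on whether study drug was interrupted or stopped.
- *It becomes serious.* Under the sponsor's always-serious list (Protocol 5.2.2.2), the serious item is ticked for the existing event, and further information goes into a follow-up report. Neither step calls for a new onset date, so it is not a TEAE.
- *It leads to stopping study drug.* Action taken is a field of the event. Nothing says that stopping drug opens a new record, so it is not a TEAE.
- *Its worsening is entered as a separate event under Protocol 5.2.2.1, dated at the worsening.* Onset is after the first dose here, so it is a TEAE.

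The documents do not say whether the rule on pre-existing conditions covers an event already open and re-entered, or how such a record is dated. Protocol 5.2.2.2 leaves detailed instructions to the Investigator Site File.

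**Step 2: see which outputs depend on the definition.**

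| Output | Place | Worded as TEAE only? |
|---|---|---|
| Overview rows for any, related, severe, serious and discontinuation TEAEs | SAP 11.2.1 | Yes |
| Overview row for related SAEs | SAP 11.2.1 | Row no, lead-in yes |
| Overview row for all deaths | SAP 11.2.1 | Row no; intent is to include all |
| By SOC and PT, by severity, by relatedness | SAP 11.2.1 | Yes |
| Rate per 100 patient-years | SAP 11.2.1 | Yes (numerator is TEAEs) |
| Discontinuation summaries by SOC and PT | SAP 11.2.2 | Yes |
| SAE summaries by SOC and PT | SAP 11.2.2 | Not stated |
| Listings of deaths, SAEs and AEs leading to discontinuation | SAP 11.2.2 | No |

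SAP 11.2.2 also lists pretreatment SAEs, defined by a start before the first study-drug injection. If that means the first injection in this study, an event that turned serious here on treatment would be labelled pretreatment.

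**Step 3: illustrate the size.** Planned N is about 100 (Protocol 3.1, SAP 4.2). The other two inputs are assumptions with no basis in the documents: 10% to 40% of patients carry over an open event, and 5% to 20% of those have a change recorded without a new onset date.

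- Low end: 100 × 0.10 × 0.05 = 0.5 patients
- High end: 100 × 0.40 × 0.20 = 8 patients

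This is an upper bound for any one row. A patient with another TEAE is already in the overall count, and a rise from mild to moderate enters none of the severe, serious or discontinuation rows.

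**The case against.** The best defence is that the protocol already handles worsening. An exacerbation of a pre-existing condition is itself an adverse event, each event has its own onset date, and a condition open at roll-over can be read as pre-existing for this trial. On that reading the worsening gets its own record and meets the SAP definition. This stands as a possibility, so a reader should not infer that every worsened carried-over event is missing from every TEAE table. It does not settle the matter, because neither document states the convention, and it does not reach a change in seriousness or a discontinuation, which are recorded as attributes of an existing event.

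A reader might also infer that these events disappear from the report. They do not: the SAP 11.2.2 listings cover deaths, all SAEs and AEs leading to discontinuation, and the SAE summaries there may include them. Listings, however, do not correct percentages or rates in the TEAE tables.

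A third inference would be that open events are the ones most likely to worsen with continued drug. The documents do not support it. Patients enter after completing 1311.2 follow-up or on loss of response from week 24, about a quarter of 1311.2 patients had no risankizumab to continue, and Protocol 3.3.3 excludes patients with a drug-related SAE in 1311.2 or with clinically significant laboratory abnormalities.

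Finally, the default for incomplete onset dates is conservative and no test is planned. Both are true, but neither supplies a rule for an event with a complete, earlier onset date.

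**Conclusion.** The point holds in a limited form and is worth correcting before database lock. SAP 11.2.1 has no worsening criterion, although events open at the end of 1311.2 are re-entered and followed. Where such an event keeps its original onset date and then rises in grade, becomes serious or leads to stopping study drug, the TEAE-restricted outputs leave it out. Whether that happens for a rise in grade depends on a recording convention that neither document states.

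The number affected is unknown, and the 0.5 to 8 patients above only shows scale under assumed inputs. The direction is clear for TEAE counts: an omission can lower them and cannot raise them. A claim of a material bias in favour of the drug would go further than the documents allow, since the size could be close to nil if sites enter worsenings as new events.

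**What to change.** In SAP 11.2.1, define a TEAE as an event with onset after the first risankizumab dose in this study, or a pre-existing event that increases in severity or becomes serious after that dose, in either case within the 105-day window. Then:

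- date the TEAE at the recorded change where that date is available. The per-event data in Protocol 5.2.2.2 do not include a date of change, so a query will be needed;
- count the change once if the site has already entered it as a new event;
- flag, in the discontinuation summary, carried-over events that lead to stopping study drug, rather than calling them treatment-emergent when nothing else has changed;
- state whether the SAE summaries in SAP 11.2.2 are limited to treatment-emergent events, and which study's first injection defines the pretreatment SAE listing.

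The cost is the SAP wording, a query on carried-over events and a programming rule. AE counts may rise slightly.

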7.3.3 Safety analyses

All subjects who received one dose of study drug will be included in the safety evaluation.

Safety analyses will focus on adverse events related to early discontinuation, immune suppression and injection site effects. AEs will be coded using the Medical Dictionary for Drug Regulatory Affairs (MedDRA). All AEs occurring up to 12 weeks after the last trial medication administration will be assigned to the treatment period for evaluation. The evaluation of adverse events will comprise various frequency tabulations. The additional analyses of pre-defined AESI will consider the frequency, intensity, time to first onset of the AE, duration of the AE and clinical consequences (e.g. study discontinuation).

Analysis of laboratory measures will similarly focus on hematologic measures of immune suppression. Descriptive statistics of laboratory values over time and for the difference from baseline will be provided. Frequency tables of changes with respect to the reference range between baseline and last/worst value on treatment and patients with possible clinically significant abnormalities will also be presented.

Immunogenicity will be evaluated in terms of time to antibody emergence starting from the time of first exposure to BI 655066 in either 1311.2 or 1311.13. This will be analysed using a Kaplan-Meier estimate.

Safety will also be assessed by evaluation of vital signs (BP, PR, RR, oral or tympanic body temperature) and local tolerability.

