### **Definition of Final Observation (Applicable to Safety Analyses)**

Final observation in the entire study is defined as the last non-missing observation collected within 105 days after the last dose of risakizumab.

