#### 4. Adverse Event per 100 Patient-years of Exposure

Adverse events occurring during the entire study will be presented by event rate per 100 patient-year.

AEs per 100 patient-years of exposure is defined as the number of AEs divided by the total exposure in 100 patient-years. Note that one event per preferred term per day per subject will be counted in the calculation of the number of AEs (i.e., a preferred term will not be counted twice on the same day for the same subject). See the calculation method below.

$$100 \times \frac{\text{Number of TEAEs}}{\text{Total Patient Years}}$$

where total patient years is defined as the sum of the study drug exposure (defined as date of last dose – date of first dose + 105 days (5 half-lives)) of all subjects normalized by 365.25, and rounded to one decimal place.

The following summaries of AEs per 100 patient-years of exposure will be generated:

- Adverse event overview
- TEAE by SOC and PT
- SAE
- Treatment emergent adjudicated CV events
- Treatment emergent malignancies
- Serious treatment emergent malignancies

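### The SAP counts adverse events to 105 days after the last dose where the protocol stops at 12 weeks; the departure is not declared, and completers are credited with person-time in which they are not observed.

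*SAP*

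**What the plan says.** **Protocol.** Section 5.2.2.2 sets the residual effect period: "The REP for BI 655066 is 12 weeks". It draws the consequence that "all events reported within 12 weeks of the last trial medication will be considered on treatment". Section 7.3.3 repeats the rule for the analysis: "All AEs occurring up to 12 weeks after the last trial medication administration will be assigned to the treatment period for evaluation". AEs are collected up to the Extended EOS visit, "which is 84 (+7 days) days after the last dose of trial medication". Sections 5.2.1.1 and 7.3.1 make the occurrence of AEs, drug-related AEs and SAEs the primary safety endpoints.

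**SAP.** Section 11.2.1 requires an onset after the first dose in this study and "with an onset date within 105 days after the last dose of study drug in the analysis period". The patient-year denominator in the same section uses "date of last dose – date of first dose + 105 days (5 half-lives". Section 6.0 defines Final Observation as "the last non-missing observation collected within 105 days after the last dose". Section 9.0 defines total risankizumab exposure as last dose date minus first dose date plus 84 days.

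Where the SAP leaves the protocol on laboratory grading (section 11.3.2, RCTC to NCI CTCAE), it says so and gives a reason. It makes no such statement about moving from 84 to 105 days.

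**The concern.** Safety is the protocol's primary objective (section 2.2), and the SAP reports the primary safety endpoints through its treatment-emergent definition. A change to that definition changes the primary result, so it should be visible and justified.

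The added 21 days are also not observed alike in all patients. For completers, AE collection ends at about the point where the protocol's window ends. Patients who stop early are followed for 12 weeks from the Extended EOT visit, not from the last dose, so they can be under observation well past day 84. The rate denominator gives everyone the same 105-day tail, whether or not anyone was watching.

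**Working it through.** **1. The protocol's figure.** 12 × 7 = 84 days, which agrees with the 84-day Extended EOS. The gap to the SAP is 105 − 84 = 21 days. Reading 105 days as five half-lives implies 105 / 5 = 21 days per half-life. Neither document states a half-life, so this cannot be checked.

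**2. Who is observed on days 85 to 105.**
- On-schedule completers: collection stops at day 84 to 91 after the last dose, so 0 to 7 of the added days are observed.
- Early discontinuers: no dose is given at an early Extended EOT (Flow Chart, footnote 10), and Extended EOS follows 84 days later. If EOT is x days after the last dose, nominal collection runs to day x + 84 and covers min(x, 21) of the added days. All 21 are covered once x is 21 or more.

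**3. Person-time.** Assume k doses in this study, 84 days apart, with the first dose in this study as origin. The SAP credits 84(k − 1) + 105 days. For a completer, 14 of these days are unobserved if EOS is on day 91, and 21 if it is on day 84.

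| Doses | Credited days | Unobserved, EOS day 91 | Unobserved, EOS day 84 |
|---|---|---|---|
| 1 | 105 | 14 (13.3%) | 21 (20.0%) |
| 5 | 441 | 14 (3.2%) | 21 (4.8%) |
| 17 | 1449 | 14 (1.0%) | 21 (1.4%) |

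A completer's rate is too low by about these percentages. Across 100 patients, the longer tail adds 100 × 21 / 365.25 = 5.7 patient-years.

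**4. Extra events (upper bound).** All of these are assumptions, except that the planned number of patients is about 100:
- 100 patients, of whom d = 10, 20 or 30 stop early;
- 1 year of observation for early stoppers and 3 years for completers;
- 150 AEs and 8 SAEs per 100 patient-years, at a constant rate r;
- every early stopper observed for all 21 added days, and every completer for 7.

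Extra events = d × r × 21/365.25 + (100 − d) × r × 7/365.25.
- d = 10: 0.86 + 2.59 = 3.45 AEs, 25% of them in early stoppers.
- d = 20: 1.72 + 2.30 = 4.02 AEs, 43% in early stoppers.
- d = 30: 2.59 + 2.01 = 4.60 AEs, 56% in early stoppers.

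Against 420, 390 and 360 AEs in total, these are 0.8%, 1.0% and 1.3%. Extra SAEs are 0.18 to 0.25.

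**5. Newly counted subjects.** The SAP overview counts subjects with at least one event, so a late event matters only if the patient had none before. With Poisson events, the chance is exp(−rT) × [1 − exp(−rw)], where T is years observed and w is the added window.
- Any AE, early stopper: exp(−1.5) × 0.0826 = 0.0184.
- Any AE, completer: exp(−4.5) × 0.0283 = 0.0003.
- Per 100 patients: 0.21, 0.39 and 0.57 for d = 10, 20 and 30.
- SAEs, by the same formula: 0.15 to 0.21.

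**6. Other AE rates.** At 50 AEs per 100 patient-years, the same formulas give 1.2 to 1.5 extra AEs and 0.4 to 0.7 new subjects. At 200 they give 4.6 to 6.1 AEs and 0.2 to 0.4 subjects.

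**7. Final Observation.** A discontinuer with EOT 1 to 21 days after the last dose has a nominal EOS sample on days 85 to 105, which the SAP would take as final. A completer with an on-schedule EOS on days 85 to 91 also has a valid sample there. A strict day-84 limit would discard it and fall back to a visit about 12 weeks earlier.

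**The case against.** The best defence is that 105 days is a reasoned choice. The SAP labels it five half-lives, applies it to both the numerator and the denominator of the rates, and so retains collected events in a trial about safety. The study is descriptive, so no test turns on it. This largely stands. The documents cannot settle which residual period is pharmacologically right, and the rate is not mismatched by definition. But the label does not acknowledge a departure from the protocol, and the denominator still includes days on which completers are no longer followed.

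Three stronger readings are tempting but not supported:

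- **A reader might infer that the longer window mainly adds events in patients who stopped early.** Per patient, early stoppers can have more of the added time observed. In total, step 4 puts 75% and 57% of the added AEs in completers at 10% and 20% discontinuation. Only at 30%, or if completers' EOS visits fall at day 84 or before, do early stoppers predominate.
- **A reader might infer that primary incidence shifts materially.** Most patients with a late AE would already be counted; step 5 gives less than one subject per 100.
- **A reader might infer that off-treatment laboratory values become final values and that day 84 should be the limit there too.** The protocol's two 12-week rules concern events. Its reference to laboratory values on treatment (section 7.3.3) carries no day limit. When a regular visit is turned into EOT at about day 84, EOS falls near day 168, outside either window.

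**Conclusion.** The conflict between the documents is real and undeclared, and it concerns the window for the primary safety endpoints. The SAP also uses two tails, 84 days for exposure and 105 for patient-years, without explaining the difference. The numerical effect is small. Rates in on-schedule completers are lowered by about 1% at 17 doses and by 13% to 20% at one dose. At most about 3.5 to 4.6 AEs and 0.2 to 0.6 subjects with any AE are added per 100 patients. The event figures rest on the assumed rates, follow-up times and discontinuation shares. They are upper bounds on observed time, because not every completer is seen as late as day 91 and not every early stopper completes follow-up. The case for correcting it is agreement with the protocol and a denominator that reflects observation, not a likely change in the safety conclusion.

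**What to change.** Reconcile Protocol 5.2.2.2 and 7.3.3 with SAP 9.0 and 11.2.1, and state in the SAP which window serves which table.

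- Report the primary incidence and rates of AEs, drug-related AEs and SAEs by onset within 12 weeks of the last dose. Match the person-time tail to that window and cap it at each patient's last observation.
- Keep the 105-day count as a labelled sensitivity table with the half-life justification written out. Cap its person-time in the same way.
- Do not impose a strict 84-day limit on Final Observation. Any change there must keep on-schedule Extended EOS samples through day 91.

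The cost is a few SAP edits before database lock and one extra set of tables. Events on days 85 to 105 would then appear only in the sensitivity table.
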